An additional 20 mL for assay development will be taken in Stage 1 on Day 85 from the participants who have given specific consent.

§ Out-of-window vaccination is not allowed.

¹ For literate participants in Europe/Africa only

² For illiterate participants in Africa only

³ The pre 2nd and 3rd vaccination screening in Malawi could take more than a day, necessitating additional site visits but not more than 72 hours prior to the actual receipt of the vaccination.

⁴ For illiterate participants, pDiary cards will be completed by the site field worker.

⁵ For illiterate participants, pDiary cards can be returned by the field worker at the end of the 7 days after administration.

⁶ For Malawi (Stage 2) only, subjects who test positive for malaria at Screening will be temporarily excluded (even if asymptomatic) and enrollment/first vaccination delayed until a negative malaria highly sensitive RDT is available. Treatment will also be provided for such prospective participants at the Investigator's discretion according to local guideline. For subsequent vaccinations, malaria RDT testing will only be performed if participants have symptoms suggestive of malaria.

⁷ Home visit for safety follow-up will take place only on Day 2.

Table 2 Intervals Between Study Visits

Interval	Planned visit interval	Allowed interval range
Screening (Day -28) → Visit 1 (Day 1)	Up to 28 days*	Up to 28 days*
Visit 1 (Day 1) → Visit 2 (Day 8)	7 days	7-10 days
Visit 1 (Day 1) → Reminder phone call 1 (Day 4)	3 days	1-3 days
Visit 1 (Day 1) → Visit 3 (Day 29)	28 days	28-33 [#] days**
Visit 1 (Day 1) → Visit 4 (Day 57)	56 days	52-62 days**
Visit 4 (Day 57) → Visit 5 (Day 64)	7 days	7-10 days
Visit 4 (Day 57) → Reminder phone call 2 (Day 60)	3 days	1-3 days
Visit 4 (Day 57) → Visit 6 (Day 85)	28 days	28-33 [#] days**
Visit 4 (Day 57) → Visit 7 (Day 169)	112 days	110-126 days**
Visit 4 (Day 57) → Visit 7 (Day 169)	112 days	110-140 ^{\$} days**
Visit 7 (Day 169) → Visit 8 (Day 176)	7 days	7-10 days
Visit 7 (Day 169) → Reminder phone call 3 (Day 172)	3 days	1-3 days
Visit 7 (Day 169) → Visit 9 (Day 197)	28 days	28-33 [#] days**
Visit 7 (Day 169) → Visit 10 (Day 337)	168 days	154-182 days

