4.5 Study Holding Criteria

4.5.1 Study Holding Rules

Holding rules will be introduced to ensure a well-controlled exposure to the investigational candidate vaccine and to prevent participants from being exposed to any unnecessary safety risks in this FIH study. The holding rules will point attention to safety signals and indicate requirements for formal committee reviews that will decide whether additional participants can be exposed to the study intervention if particular criteria are met. Study holding rules are defined in [Table 5](#).

Holding rule 1 and 2c (threshold ≥ 1) will be assessed by the Investigator on a continuous basis irrespective of the number of enrolled participants and meeting any of these holding rules will trigger a hold of study intervention administration irrespective of number of enrolled participants and/or timing of the event relative to study intervention administration. Holding rule 2 (2a-b) and 1d.2 in Stage 2 (threshold ≥ 2) will be assessed during the safety evaluations on blinded or unblinded data.

These holding rules have been written under the assumption that the safety data from all participants will be available. If the data from some participants are not available (eg, in case a participant is lost to follow-up), then the holding rules will be assessed on a pro-rata basis.

If the Investigator becomes aware of a holding rule being met, he/she must suspend administration of the study intervention and inform the Sponsor's delegate immediately (holding rules 1a-d and 2c).

However, for the other holding rules (1d.2 in Stage 2, 2a and 2b) which have a threshold ≥ 2 , the Investigator will inform the Sponsor's delegate immediately, without suspending the administration of the study intervention.

The Sponsor's delegate will inform the Investigator if holding rules 1d.2 in Stage 2 and 2a-b are met.

The following communication sequence must be followed:

- The concerned site staff has to put study intervention administration on hold.
- The concerned site staff must immediately inform IQVIA CRA and Medical Monitor (contact details will be provided in a separate document) via email and phone communication who will in-turn inform the GVGH Study Responsible Project Physician.
- All informed site staff will confirm to their local contact that action has been taken providing appropriate documentation to GVGH through the IQVIA CRA and Medical Monitor.

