- GSK will further evaluate the case with the iSRC and GSK Global Safety Board and will take the decision to stop or to restart the study intervention administration. GVGH project physician will inform the IQVIA project lead of the decision and the rationale for the decision and all site staff will be informed about that final decision by IQVIA project lead.

Table 5 Study Holding Rules

Events	Number or % of participants needed to pause administration of study intervention	
	Stage 1 Step 1 and Step 2	Stage 2
1a Death or any life-threatening SAE regardless of causality	≥1	≥1
1b Any non-life-threatening SAE that cannot be reasonably attributed to another cause other than study intervention administration	≥1	≥1
1c Any withdrawal from the study (by Investigator or participant request) following a Grade 3 AE that cannot be reasonably attributed to another cause other than study intervention administration	≥1	≥1
1d.1 Any administration site or general solicited event leading to hospitalization, OR Necrosis at the injection site, each within the 7-day (Days 1 to 7) post-administration period	≥1	≥1
1d.2 Fever >40°C (104°F) within the 7-day (Days 1 to 7) post-administration period	≥1	≥2
2a Any Grade 3 solicited administration site event (lasting 48 h or more) in an investigational group, within the 7-day (Days 1 to 7) post-administration period	≥2	NA
2b Any Grade 3 solicited general AE (lasting 48 h or more) in an investigational group, within the 7-day (Days 1 to 7) post-administration period	≥2	NA
2c Any Grade 3 unsolicited AE in an investigational group, that can be reasonably attributed to the study intervention administration, within the 7-day (Days 1 to 7) post-administration period or Any Grade 3 abnormality in prespecified hematological or biochemical laboratory parameters in an investigational group within the 7-day (Days 1 to 7) post-administration period	≥1	NA

Abbreviations: AE = adverse event; h = hours; SAE = serious adverse event; NA = not applicable

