8.1.2 Laboratory Assays

All laboratory testing will be performed using characterized and fit-for-purpose qualified assays as indicated in [Table 9](#) at GVGH laboratory or in a laboratory designated by GVGH.

Table 9 **Laboratory Assays**

Assay type	System	Sampling time points	Component	Method	Unit of measure	Number of participants
Humoral Immunity (Antibody determination)	Serum	Stage 1 Days 1, 29, 57, 85, 169 and 197	Anti- S. Typhi Vi Ag total IgG	ELISA	EU/mL [#]	50 (Stage 1) 105 (Stage 2)
		Stage 2 Days 1, 29, 57, 85, 169 and 197	Anti- S. Typhimurium O Ag total IgG		EU/mL	
			Anti- S. Enteritidis O Ag total IgG		EU/mL	
Clinical Safety	Whole blood	Screening: Day -28 to Day -1 Stage 1 Days 1, 8, 29, 57, 64, 85, 169, 176 and 197 Stage 2 Days 1, 8, 29, 57, 64, 85, 169, 176 and 197	Leukocytes (white blood cells) Eosinophils Basophils Neutrophils Monocytes Lymphocytes Erythrocytes (red blood cells) ^s Hemoglobin Hematocrit ^s Platelets Prothrombin time ^{s, **}	Hematology panel		155 (Screening) 50 (Stage 1) 105 (Stage 2)
	Serum/whole blood	Screening: Day -28 to Day -1 Stage 1	Total bilirubin ^s Aspartic Aminotransferase Alanine Aminotransferase γ-Glutamyl Transferase ^s	Biochemistry		155 (Screening) 50 (Stage 1) 105 (Stage 2)

Assay type	System	Sampling time points	Component	Method	Unit of measure	Number of participants
		Days 1, 8, 29, 57, 64, 85, 169, 176 and 197 Stage 2 Days 1, 8, 29, 57, 64, 85, 169, 176 and 197	Lactic Dehydrogenase ^s Alkaline Phosphatase ^s Total Proteins ^s Glycosylated hemoglobin (HbA1c) ^s Urea/Blood Urea Nitrogen Creatinine Sodium ^s Potassium ^s			
	Serum	Screening: Day -28 to Day -1	HBsAg HCV antibodies HIV antibodies	Serology for virology		155 (Screening)
	Urine	Screening: Day -28 to Day -1 Stage 1: Days 1, 57 and 169 Stage 2: Days 1, 57 and 169	Human chorionic gonadotropin	Pregnancy test		NK (Stage 1) NK (Stage 2)
	Urine	Screening	Urinalysis	Dipstick		155 (Screening)
	Serum	Screening	Human leukocyte antigen B27*	PCR		50 (Stage 1, Screening)

Abbreviations: Ab = Antibody; CCI [REDACTED]; IgG = Immunoglobulin G; EU = ELISA Units; ELISA = enzyme-linked immunosorbent assay; GVGH = GlaxoSmithKline Biological SA Vaccines Institute for Global Health; HBsAg = hepatitis B surface antigen; HCV = hepatitis C virus; HIV = human immunodeficiency virus; NK = Not Known; PCR = polymerase chain reaction; ^s = test performed only during Screening period; CCI [REDACTED]; CCI [REDACTED]

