In Step 2, a second sentinel of 10 participants vaccinated on consecutive days. They will receive a phone call for safety surveillance on the day following the first study intervention administration (Day 2), before proceeding with study intervention administration in the subsequent participants. The remaining 30 participants will be vaccinated at least 60 minutes apart.

Likewise, in Stage 2, the first 21 participants will receive the study interventions sequentially, at least 60 minutes apart, with a safety phone call/home Visit the day after administration for safety surveillance.

All 155 participants in the study (Stage 1 and Stage 2) will be closely monitored at the site for at least 60 minutes post-administration for safety surveillance.

Seven days after the first study intervention administration in the low dose cohort (Step 1) in Stage 1 is completed, an iSRC will receive a summary of all available safety data (solicited administration site events and systemic events, unsolicited AEs and SAEs) and listings of hematology and blood chemistry test values obtained following the first study intervention administration (baseline and 7 days after study intervention administration). Based on evaluation of the safety data (review #1, [Table 14](#)), the iSRC will make a recommendation, as to whether the next stage of the trial (Stage 1/Step 2), when the administration of the full dose of the study interventions to the study participants, should start.

Seven days after all participants in Stage 1/Step 1 have received their second study intervention, there will be an iSRC review of all safety data collected up to day 7 after second administration (Day 64) in Step 1 (review #2, [Table 14](#)). If there is no safety concern with any of the investigational groups, the second study intervention administration in Stage 1/Step 2 can commence.

There will be another iSRC data review 28 days after the second administration in Stage 1/Step 2 (review #3, [Table 14](#)). In the case of a favorable review, recruitment of participants in Stage 2 in Africa can commence.

All the participants in Stage 1 will complete the trial according to the schedule. A final safety evaluation of all data collected in Stage 1 will be performed once the study is completed.

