
 • Any clinically significant abnormal laboratory findings or other abnormal safety assessments which are associated with the underlying disease, unless judged by the Investigator to be more severe than expected for the participant's condition. • Pre-existing conditions or signs and/or symptoms present in a participant before the first dose of study intervention. These events will be recorded in the medical history section of the eCRF. • Situations in which an untoward medical occurrence did not occur (eg, social and/or convenience admission to a hospital). • Anticipated day-to-day fluctuations of pre-existing disease(s) or condition(s) present or detected at the start of the study that do not worsen. • Hospitalization for elective treatment of a pre-existing condition (known or diagnosed before signing the informed consent) that did not worsen from baseline.

Definition of SAE

An SAE is defined as any untoward medical occurrence that, at any dose:
a) Results in death
b) Is life-threatening
The term 'life-threatening' in the definition of "serious" refers to an event in which the participant was at risk of death at the time of the event. It does not refer to an event, which hypothetically might have caused death, if it were more severe.
c) Requires inpatient hospitalization or prolongation of existing hospitalization
In general, hospitalization signifies that the participant has been detained (usually involving at least an overnight stay) at the hospital or emergency ward for observation and/or treatment that would not have been appropriate in the physician's office or outpatient setting. Complications that occur during hospitalization are AEs. If a complication prolongs hospitalization or fulfills any other serious criteria, the event is serious. When in doubt as to whether "hospitalization" occurred or was necessary, the AE should be considered serious.
Hospitalization for elective treatment of a pre-existing condition that did not worsen from baseline is not considered an AE.
d) Results in persistent disability/incapacity

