Appendix 7 Grading Scales for Hematology and Biochemistry Safety Laboratory Assessments

The details of grading scales are provided in [Table 19](#) and [Table 20](#).

Table 19 Stage 1 – Adults (Europe)

Laboratory test	Mild (Grade 1)	Moderate (Grade 2)	Severe (Grade 3)	Potentially life--threatening (Grade 4)
Creatinine – mg/dL (male)	>1.17 – 1.7	>1.7 – 2.0	>2.0 – 2.5	>2.5 or requires dialysis
Creatinine – mg/dL (female)	>0.96 – 1.7	>1.7 – 2.0	>2.0 – 2.5	>2.5 or requires dialysis
Liver Function Tests –ALT, AST increase by factor	$\geq 1.1 - 2.5 \times$ ULN	$>2.5 - 5.0 \times$ ULN	$>5.0 - 10 \times$ ULN	$>10 \times$ ULN
Hemoglobin (female) - g/dL	11.0 – <11.8	9.5 – <11.0	8.0 – <9.5	<8.0
Hemoglobin (female/male) change from baseline value - g/dL	Any decrease – 1.5	>1.5 – 2.0	>2.0 – 5.0	>5.0
Hemoglobin (male) - g/dL	12.5 – <12.9	10.5 – <12.5	8.5 – <10.5	<8.5
WBC Increase - cell/mm ³	>9300 – 15000	>15000 – 20000	>20000 – 25000	>25000
WBC Decrease - cell/mm ³	2500 – <3650	1500 – <2500	1000 – <1500	<1000
Platelets Decreased - cell/mm ³ (male)	125000 – <149000	100000 – <125000	25000 – <100000	<25000
Platelets Decreased - cell/mm ³ (female)	125000 – <171000	100000 – <125000	25000 – <100000	<25000
Neutrophils Decrease - cell/mm ³	1500 – <1573	1000 – <1500	500 – <1000	<500
Lymphocytes decrease cell/mm ³	750 - <1133	500 - <750	250 - <500	<250
Eosinophils Cell/mm ³	>273 - 1500	>1500 - 5000	>5000	Hypereosinophilic

Abbreviations: ALT=alanine aminotransferase; AST = aspartate aminotransferase; ULN=upper limit of normal; WBC=white blood cell

The grading scale has been adapted from the Food and Drug Administration (FDA) Guidance for Industry- Toxicity Grading Scale for Healthy Adult and Adolescent Volunteers Enrolled in Preventive Vaccine Clinical Trials [[US Department of Health and Human Services](#), 2007] and adjusted considering local reference ranges provided by the site. Parameters not included in the FDA grading scales will not be graded; their assessment will be based on laboratory reference ranges and medical judgment.

Table 20 Stage 2 – Adults (Africa)

Laboratory test	Mild (Grade 1)	Moderate (Grade 2)	Severe (Grade 3)	Potentially life- threatening (Grade 4)

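### Stage 1 holding rule 2c: read literally, the laboratory limb omits Grade 4 and its window misses every scheduled 7-day safety sample, so there is no clear immediate hold within a step

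*Protocol*

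**What the plan says.** Rule 2c applies in Stage 1 only, with a threshold of one participant; Table 5 marks it not applicable in Stage 2. It has two limbs: a Grade 3 unsolicited AE attributable to the intervention, and "Any Grade 3 abnormality in prespecified hematological or biochemical laboratory parameters in an investigational group within the 7-day (Days 1 to 7".

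Table 19 in Appendix 7 grades Stage 1 laboratory values from 1 to 4 in bands that do not overlap. One row reads "Creatinine – mg/dL (male) >1.17 – 1.7 >1.7 – 2.0 >2.0 – 2.5 >2.5 or requires dialysis".

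Table 9 in Section 8.1.2 schedules the safety bloods: "Stage 1 Days 1, 8, 29, 57, 64, 85, 169, 176 and 197". Table 2 in Section 1.3 gives the allowed interval for the first 7-day visit: "Visit 1 (Day 1) → Visit 2 (Day 8) 7 days 7-10 days". The same 7-10 day range applies to Visits 5 and 8.

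The text of Section 4.5.1 says that meeting rule 1 or 2c triggers a hold "irrespective of number of enrolled participants and/or timing of the event relative to study intervention administration".

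For the move to the full dose, Section 9.7 has iSRC review #1 receive "listings of hematology and blood chemistry test values obtained following the first study intervention administration (baseline and 7 days after study intervention administration").

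**The concern.** This is the first-in-human stage, and the second limb of 2c is the rule written specifically for laboratory toxicity. Taken as worded, it has two gaps.

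- **Grade.** It stops dosing for a severe value but does not name a potentially life-threatening one.
- **Window.** It closes the day before the earliest scheduled sample that could show either.

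If a site follows Table 5 literally, only an unscheduled test could trigger the limb. If it follows the timing sentence in Section 4.5.1, the 7-day sample would count. The people affected are those in the same step still waiting for a dose when an early participant's 7-day result comes back.

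**Working it through.** **1. The plan's own figures for 2c.** The text under Figure 2 treats 2c as a rule met by one event, so P(met) = 1 − (1 − p)^n.

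- n = 10: not met at 1% = 0.99^10 = 90.4% (stated: more than 90%). Met at 10% = 1 − 0.90^10 = 65.1% (stated: more than 65%). Both reproduce.
- n = 40: not met at 1% = 0.99^40 = 66.9% (stated: more than 70%). Met at 2.5% = 1 − 0.975^40 = 63.7% (stated: more than 65%). The first misses by about 3 points. That is a separate matter, and nothing below depends on it.

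These figures assume that events can be observed. Under the literal window, scheduled laboratory samples contribute nothing to them.

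**2. Window against schedule.** Section 8.3.5 sets out the 7-day follow-up after each dose as the dosing day plus six days. The visit falls 7 to 10 days after dosing.

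| Dose day | Window (d to d+6) | 7-day sample (d+7 to d+10) | Inside? |
|---|---|---|---|
| 1 | 1–7 | 8–11 | No |
| 57 | 57–63 | 64–67 | No |
| 169 | 169–175 | 176–179 | No |

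No scheduled 7-day sample out of three can fall inside the window, and the 28-day samples are later still. Only the additional tests allowed by Section 8.2.2 could.

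**3. Grade.** A male creatinine of 2.3 mg/dL lies in the Grade 3 band (above 2.0 to 2.5) and meets the laboratory limb. A value of 2.8 mg/dL lies in Grade 4 (above 2.5) and, read literally, does not.

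**4. What the other rules catch.**

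- First limb of 2c: Appendix 3 makes a clinically significant laboratory abnormality an AE, and unsolicited AE intensity stops at Grade 3. A very high value judged severe and related can therefore qualify, but only within the same Days 1 to 7.
- Rule 1a: "Death or any life-threatening SAE regardless of causality". Appendix 3 requires actual risk of death at the time: "It does not refer to an event, which hypothetically might have caused death, if it were more severe". A Grade 4 label alone is not enough.
- Rule 1b: no window, but the value must be judged an SAE with no other reasonable explanation.
- Rule 1c: no window and no seriousness requirement, but the participant must withdraw.

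A non-serious Grade 3 or 4 value at the 7-day visit, in a participant who stays in the study, is left without a clear rule.

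**5. Who is still undosed.** Sentinel k is dosed on step day k, so the first sentinel's sample is drawn on step day 8 (1 + 7) to 11 (1 + 10).

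- Day 8, before that day's dosing: 7 have been dosed, leaving 33 of 40 in Step 2 (82.5%) and 3 of 10 in Step 1.
- Day 11, if the remaining 30 have not started: 10 have been dosed, leaving 30 of 40 (75%) in Step 2 and 0 of 10 in Step 1.

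These counts are at blood draw. Turnaround is not stated. With a day 8 sample and an assumed 0, 1, 2 or 3 days to result, 33, 32, 31 or 30 remain in Step 2. In a less favourable case, assume a day 11 sample, the remaining 30 dosed at 8 per day from day 11, and a result on the morning of day 13. Then 10 + 16 = 26 have been dosed and 14 of 40 (35%) remain.

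**6. Holds after the change.** The documents give no background rate of Grade 3 or higher values, so p is assumed per participant per dose. The chance of at least one hold per dosing round is 1 − (1 − p)^n. Groups receiving investigational vaccine number 4 + 4 = 8 in Step 1 and 16 + 16 = 32 in Step 2.

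| p | Step 1, n = 8 | Step 1, n = 10 | Step 2, n = 32 | Step 2, n = 40 |
|---|---|---|---|---|
| 0.5% | 3.9% | 4.9% | 14.8% | 18.2% |
| 1% | 7.7% | 9.6% | 27.5% | 33.1% |
| 2.5% | 18.3% | 22.4% | 55.5% | 63.7% |
| 5% | 33.7% | 40.1% | 80.6% | 87.1% |

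**The case against.** The strongest reply is that Section 4.5.1 names 2c, has it assessed continuously, and makes timing irrelevant. The protocol also repeatedly describes Days 8, 64 and 176 as 7 days after dosing, and Section 9.7 equates Day 64 with day 7 after the second dose. On this view the window is a one-day labelling slip, and no sensible site would ignore a Grade 4 value while holding for a Grade 3.

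That is probably the intent, and many investigators would act on it. It does not settle the text. A rule must first be met, and Section 4.5.1 sends the reader to Table 5 for the definitions. The timing sentence also covers rules 1d.1 and 1d.2 in Stage 1, which carry the same window. If it cancelled windows, it would cancel theirs too.

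Three stronger readings are tempting and not supported.

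- *Escalation to the full dose is unprotected.* It is not. iSRC #1 sees the Step 1 7-day laboratory listings before the first full dose, and iSRC #2 sees Step 1 data to Day 64 before the second. Ad hoc reviews may be called, and Section 5.5 ties each participant's second and third doses to their latest laboratory results.
- *No other single-event rule reaches laboratory toxicity.* Rules 1b and 1c and the first limb of 2c each reach part of it. Appendix 3 also says important medical events should usually be treated as serious and lists blood dyscrasias, so many Grade 4 hematology values could fall under 1b.
- *The blinded Investigator cannot apply a rule limited to investigational groups, so that phrase should go.* Section 4.5.1 already has the site hold and the case go to the iSRC, which reviews unblinded data. Deleting the phrase would add holds triggered by placebo participants.

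The safeguards still leave a gap inside Step 2. Table 14 plans no review between the 10 sentinels and the remaining 30, and ad hoc review is discretionary.

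**Conclusion.** The point holds in a limited form. Read literally, the laboratory limb of 2c names Grade 3 but not Grade 4, and no scheduled post-dose sample can trigger it. Section 4.5.1 contains text that conflicts with this, and nothing says which governs. The consequence is the absence of a clear immediate hold within a step for a non-serious Grade 3 or 4 value, mainly for first full doses in Step 2.

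The 30 to 33 of 40 is a count at the time of the first sentinel's blood draw, assuming one sentinel per day and that the remaining 30 have not begun. A reader might take it as the number a hold would protect. The documents do not support that, because the trigger is a result and turnaround is not given.

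The scope is the 50 Stage 1 participants. The current amendment's summary refers to deviations already seen in Stage 1, so some or all of this dosing may be past.

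**What to change.** In Table 5, change the laboratory limb of 2c to *Grade 3 or higher*, and extend its window to include the scheduled 7-day visit sample (Visits 2, 5 and 8, taken 7 to 10 days after dosing). For these samples this also removes the conflict with Section 4.5.1. Leave the investigational-group wording as it is.

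The cost is a few words and some extra pauses. The limb has no attribution condition, and Table 19 makes a hemoglobin fall of more than 2.0 g/dL Grade 3, so an unrelated fall could stop dosing. At the assumed 1% rate, the Step 1 figures and the Step 2 figure for investigational groups stay within the tolerance Figure 2 states for 2c (under 10% with 10 participants, under 30% with 40). The Step 2 figure counting all 40 exceeds it by about 3 points. At higher background rates pauses would be frequent, so the sponsor should check the expected rate.

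If Stage 1 dosing is complete, the sponsor should check how any Grade 3 or 4 values at Days 8, 64 and 176 were handled, and correct the wording before the rule is reused.
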